Objective(s): The primary objective of this study is to provide treatment with lyophilized S95014 in pediatric patients with ALL who completed the CL2-95014-002 study during the induction phase. Secondary objective is to assess the safety profile of lyophilized S95014 during the consolidation phase.	
Methodology: This is a multicentre, non-randomized roll-over study of lyophilized Pegaspargase (Oncaspar®, S95014) formulation in the treatment of pediatric patients with ALL. This study is designed to provide continued access to S95014 during the consolidation phase in patients who completed the CL2-95014-002 study and who are clinically benefitting from S95014 without major toxicity.	
Written informed consent and assent (when appropriate) will be obtained from each patient and/or his/her parent(s)/legal representative during the inclusion visit, corresponding to the withdrawal visit of the initial CL2-95014-002 study. Safety assessment including laboratory tests, ECG, cardiac imaging and pregnancy test performed during the withdrawal visit of the initial CL2-95014-002 study can be used to assess the inclusion in this roll-over study.	
The study duration will be approximately 7 months, including the treatment period consisting of the consolidation phase (approximately 6 months) and the follow-up period (30 days after the last S95014 infusion). After completing the consolidation phase, patient will be discontinued from the study and will be treated as per investigator's judgment.	
Lyophilized S95014 will be administered IV, over 1 to 2 hours, every two weeks during the consolidation phase at the dose of 1000, 2000 or 2500 U/m ² , as per investigator's judgment. Patients will be administered 9 infusions of lyophilized S95014, at week 7, 9, 11, 15, 17, 19, 23, 25 and 27 (3 phases S1, S2 and S3). Patients will receive other backbone chemotherapy agents as per ALL-MB 2015 protocol.	
Secondary objective of this roll-over study is to assess the safety profile of lyophilized S95014 during the consolidation phase. All adverse events regardless of grade or causality and severity will be collected after the	

Name of the sponsor: I.R.I.S.
Name of Finished Product: Lyophilized pegaspargase
Name of Active Ingredient: Pegaspargase S95014 Oncaspar®
informed consent is signed and during the entire treatment period.
Number of included participants: Planned: Approximately 88
Diagnosis and main criteria for inclusion:

Inclusion criteria
 
 - Patient who completed the CL2-95014-002 study - Patient currently receiving clinical benefit from previous treatment with S95014 as per investigator's judgment - Signed informed consent and assent, when appropriate - Highly effective contraception method

Non-inclusion criteria:
 
 - Unlikely to cooperate in the study - Pregnant and lactating women - Participant already enrolled in the study (informed consent signed) - Prior surgery or bone marrow transplant related to the studied disease - History of sensitivity to polyethylene glycol (PEG) or PEG-based drugs - Psychiatric illness/social situation that would limit compliance with study requirements - Group "E" and "T-HR" patients according to ALL-MB 2015 protocol classification - Major safety issue due to previous S95014 administration (e.g. non recovery of safety parameters, serious hypersensitivity, serious pancreatitis, serious haemorrhage, serious thromboembolic event) - Significant laboratory abnormality or uncontrolled intercurrent illness (e.g. life-threatening acute tumor lysis syndrome, symptomatic congestive heart failure, cardiac arrhythmia, severe or uncontrolled active acute infection) likely to jeopardize the patients' safety or to interfere with the conduct of the study, in the investigator's opinion
Test drug: Lyophilized S95014 reconstituted will provide 5 mL of extractable volume with the concentration of 750 U/mL. The vial of lyophilized powder (3.750 U/vial) is reconstituted with 5.2 mL of SWFI to obtain a 750 U/mL solution for single use.
Lyophilized S95014 will be administered IV every two weeks at the dose of 1000, 2000 or 2500 U/m ² , as per investigator's judgment. Patients will receive other backbone chemotherapy agents as per ALL-MB 2015 protocol .
Comparator: None
Duration of treatment: Active treatment period: 6 months
Follow-up period: 30 days
Criteria for evaluation:

Safety measurement: Safety assessments will be performed and reported throughout the study. This will include:
 
 - adverse events (AEs), treatment emergent adverse events (TEAEs), adverse events of special interest (AESI) assessments - physical examinations, performance status - laboratory assessments including haematology, blood biochemistry, urinalysis and coagulation parameters - vital signs measurements - pregnancy test for women of childbearing potential

Name of the sponsor: I.R.I.S.
Name of Finished Product: Lyophilized pegaspargase
Name of Active Ingredient: Pegaspargase S95014 Oncaspar®

- Recording of any change or addition of a new concomitant treatment 
Adverse events will be collected regardless of grade or study drug relationship and will be graded according to current NCI CTCAE criteria 5.0.
 
Safety analysis: descriptive summaries of demographic and baseline characteristics with a description of patient disposition and listing of medical history will be provided. The number and percentage of patients with adverse events will be tabulated by system organ class and preferred term.

Data Monitoring Committee: Not applicable

Contractual signatories

I, the undersigned, have read the foregoing protocol and the "Participant information and consent form" document attached to the protocol and agree to conduct the study in compliance with such documents, Good Clinical Practice (GCP) and the applicable regulatory requirements.

COORDINATOR:

NAME	
CENTER NUMBER	
DATE	
SIGNATURE	

HEAD OF LATE STAGE AND LIFE CYCLE MANAGEMENT DEPARTMENT:

NAME	[REDACTED]
DATE	[REDACTED]
SIGNATURE	[REDACTED]

Other sponsor's signatories	
BIOSTATISTICS HEAD:	
NAME	[REDACTED]
DATE	17/01/2020
SIGNATURE	[REDACTED] [REDACTED]

Table of contents

Table of contents	7
1. ADMINISTRATIVE STRUCTURE OF THE STUDY.....	16
2. BACKGROUND INFORMATION	16
2.1. Overview of disease epidemiology and current treatment	16
2.2. S95014	16
2.2.1. Mechanism of action of S95014	16
2.2.2. Pegylated asparaginase development and status	17
2.2.3. Development of a lyophilized S95014 formulation	17
2.2.4. Study rationale and design	18
3. STUDY OBJECTIVES AND ENDPOINTS.....	18
4. STUDY DESIGN	18
4.1. Investigational plan.....	18
4.1.1. Study plan.....	18
4.1.2. Investigation schedule	20
4.2. Measures to minimise bias	22
4.3. Study products and blinding systems	22
4.3.1. Products administered	22
4.3.2. IMP management	23
4.3.3. Management of blinding systems.....	24
4.4. Discontinuation of the study or temporary halt	24
4.4.1. Premature discontinuation of the study or temporary halt	24
4.4.2. Premature discontinuation of the study in an investigator site (early site closure).....	24
4.4.3. Discontinuation of the study in the event of objective reached	25
4.5. Source data	25
5. INCLUSION AND WITHDRAWAL OF PARTICIPANTS	25
5.1. Inclusion criteria	25
5.2. Non-inclusion criteria	25
5.2.1. General criteria.....	25

CoV	: Coefficient of Variation
CRA	: Clinical Research Associate
CRF	: Case Report Form
CRO	: Contract Research Organisation
CSR	: Clinical Study Report
CTCAE	: Common Terminology Criteria for Adverse Events
CV	: Curriculum Vitae
DAP	: Data Analysis Plan
DPO	: Data Protection Officer
ECG	: ElectroCardioGram
ECOG	: Easter Cooperative Oncology Group
eCRF	: Electronic Case Report Form
EEA	: European Economic Area
e.g.	: Exempli gratia (for example)
ELISA	: Enzyme-Linked Immunosorbent Assays
EMA	: European Medicines Agency
ERIN	: Event Requiring Immediate Notification
EU	: European Union
FAS	: Full Analysis Set
FDP	: Fibrin Degradation Product
g	: gram

G/L	: Giga (10^9) per litre
GCP	: Good Clinical Practice
GGT	: Gamma-Glutamyl Transferase (Gamma-Glutamyl Transpeptidase)
GMR	: Geometric Mean Ratio
h	: hour
HBs	: Surface antigen of Hepatitis B virus
HCV	: Hepatitis C virus
HDL	: High-Density Lipoprotein
HEV	: Hepatitis E virus
HIV	: Human Immunodeficiency Virus
HR	: Heart Rate
I.R.I.S.	: Institut de Recherches Internationales Servier
ICF	: Informed Consent Form
ICH	: International Conference on Harmonisation
ICTR	: International Centre for Therapeutic Research
i.e.	: id est (that is)
IEC	: Independent Ethics Committee
IMP	: Investigational Medicinal Product: a pharmaceutical form of an active ingredient or placebo being tested or used as a reference in a clinical trial (test drug / placebo / reference product)
INR	: International Normalized Ratio
IU	: International Unit
IV	: IntraVenous (route)
kg	: kilogram
L	: Litre
LDH	: Lactate DeHydrogenase
LDL	: Low-Density Lipoprotein
LVEF	: Left Ventricular Ejection Fraction
MAH	: Marketing Authorization Holder
MedDRA	: Medical Dictionary for Regulatory Activities
MRI	: Magnetic Resonance Imaging
MUGA scan	: Multi-Gated Acquisition scan
NCCN	: National Comprehensive Cancer Network
NCA	: Non-Compartmental Analysis
NCI	: National Cancer Institute
NGO	: Non-Governmental Organization
NIMP	: Non-Investigational Medicinal Product (backbone regimen used in the frame of ALL-MB 2015 protocol)
μ mol	: micromole
mg	: milligram
min	: minute
mL	: milliliter
NA	: Not Applicable
PAA	: Plasma Asparaginase Activity
PCR	: Polymerase Chain Reaction
PEG	: PolyEthylene Glycol
PD	: PharmacoDynamics

PK	:	PharmacoKinetics
PKAS	:	Pharmacokinetic Analysis Set
PS	:	Performance Status
PT	:	Prothrombin Time
RBC	:	Red Blood Cells
RNA	:	Ribonucleic Acid
SAE	:	Serious Adverse Event
SAP	:	Statistical Analysis Plan
SAS	:	Safety Analysis Set
SD	:	Standard Deviation
sec	:	second
SmPC	:	Summary of Product Characteristics
SWFI	:	Sterile Water for Injection
$t_{1/2z}$:	terminal half-life
test drug	:	Drug substance in a given dosage form, tested in a clinical trial. In this study, it corresponds to S95014 product
tmax	:	time corresponding to Cmax
TSH	:	Thyroid Stimulating Hormone
US	:	United States
V	:	Visit
WBC	:	White Blood Cells
WHO-Drug	:	World Health Organization Drug Dictionary
WOCBP	:	Woman of Child Bearing Potential

1. ADMINISTRATIVE STRUCTURE OF THE STUDY

Non sponsor parties, sponsor(s) parties and CRO responsible for local management of the study are described in a separate document entitled Administrative part of clinical study protocol.

The list of investigators is described in a separate document attached to the protocol and entitled "List of investigators".

2. BACKGROUND INFORMATION

2.1. Overview of disease epidemiology and current treatment

Leukemia is the most common pediatric malignancy. Acute lymphoblastic leukemia (ALL) is typically characterized by the proliferation of large number of immature lymphoid cells in the bone marrow, peripheral blood and other organs. ALL is the most common type (46.6%) of acute leukemia in childhood and the most commonly diagnosed cancer in children (25%) (Esparza, 2005; Noone et al, 2018). Approximately 1000 children are newly diagnosed with ALL each year in Russia (Kaprin, 2019).

The treatment of ALL includes long-term use of multiagent chemotherapy ([National Comprehensive Cancer Network clinical practice guidelines](#)), of which asparaginase is a cornerstone component (Hoelzer D et al, 2016, Asselin B et al, 1999). Asparagine is a nonessential amino acid for normal cell growth but is considered essential for leukaemic cells as these cells are dependent on exogenous sources of asparagine for survival. Asparaginase selectively kills leukaemic cells by depleting asparagine levels. (Asselin B et al, 1999). Native *Escherichia coli*-derived L-asparaginase (*E. coli* L-asparaginase) is one of the asparaginase preparations that have been used for the treatment of ALL since 1970s; however, its use is associated with high immunogenicity, which can be manifested by the occurrence of hypersensitivity reactions (Silverman LB et al, 2010) and/or the neutralization of asparaginase activity without any signs of hypersensitivity (i.e. silent inactivation) (Tong WH et al, 2014). Moreover, *E. coli* L-asparaginase must be administered frequently (i.e. three times weekly), as the drug has a very short elimination half-life (Asselin B et al, 1999).

Consequent to these limitations, pegylated formulations of *E. coli* L-asparaginase have been developed, including pegaspargase (Oncaspar®) [with a succinimidyl succinate linker].

The worldwide standard treatments for pediatric ALL include the treatment protocols established by the Children's Oncology Group (COG) and the Berlin-Frankfurt-Munster (BFM) group. In Russia, approximately 90% of newly-diagnosed pediatric patients with ALL are treated in compliance with the ALL-MB 2015 protocol (see [Appendix1](#)).

2.2. S95014

Detailed information on the nonclinical and clinical experience with S95014 is provided in the latest version of the [Investigator's Brochure](#).

2.2.1. Mechanism of action of S95014

The mechanism of action of L-asparaginase is the enzymatic cleavage of the amino acid asparagine into aspartic acid and ammonia, with subsequent depletion of asparagine in the blood plasma. Since lymphoblastic tumor cells, unlike healthy cells, appear to be unable to synthesize asparagine, the asparagine depletion results in inhibition of cell protein synthesis and therefore in their destruction.

Hence, when plasma levels of L-asparagine decrease, intracellular levels of L-asparagine become markedly low, protein synthesis is inhibited, and leukemic cells undergo apoptosis. Unless an extracellular supply of L-asparagine is available, L-asparaginase is a specific chemotherapeutic agent for leukemic cells while preserving non-leukemia cells. The goal of asparaginase therapy is sustained systemic depletion of asparagine.

2.2.2. PEGylated asparaginase development and status

Oncaspar® (pegaspargase; S95014) is a variation of the enzyme L-asparaginase modified by covalently bonding units of monomethoxy polyethylene glycol (PEG) to the enzyme, forming the active pharmaceutical ingredient PEG-L-asparaginase.

In the United States (US), S95014 received approval in 1994 for second-line use in acute lymphoblastic leukaemia (ALL) following the development of hypersensitivity to native L-asparaginase. In 2006, the US authorization of S95014 was expanded to include first-line treatment of ALL.

Pegaspargase is now very well established in clinical practice in the first-line treatment of ALL and is licensed in many countries ([Heo YA et al, 2019](#)). It has been determined by the World Health Organization (WHO) an essential medication needed to meet the needs of a health system and is included in the List of Essential Medicines (WHO 2019).

The safety profile of pegaspargase has also been well characterized over these last 25 years of consistent use in ALL treatment protocols. The most common (>5%) grade ≥ 3 AEs included hepatotoxicity (elevated transaminases, increased bilirubin and hypoalbuminemia), febrile neutropenia, hypertriglyceridemia, hyperglycemia, pancreatitis, coagulopathy, embolic and thrombotic events, and hypersensitivity. For further details, please refer to the last version of the [Investigator's Brochure](#).

So far, S95014 is not approved yet in Russia and the product is only available through a non-governmental organization (NGO) special request. Thus, patients treated in ALL-MB 2015 protocol are administered S95014 during the induction phase (one dose) and native L-asparaginase during the consolidation phase. Once approved, S95014 is expected to play an important role in Russia as a first-line treatment for ALL.

2.2.3. Development of a lyophilized S95014 formulation

Different formulations containing different quantitative and qualitative compositions of cryoprotectants were investigated to identify the best product composition that could withstand the lyophilization process and guarantee the production of high-quality drug product with improved stability. The lyophilized S95014 powder for Injection is provided in a single-use vial which after reconstituted will contain 3,750 U/5mL of active PEGylated L-asparaginase [750 U/mL after reconstitution with 5.2 mL of sterile water for injection (SWFI)], which is equivalent to the strength of liquid S95014. The lyophilized S95014 formulation has a longer shelf-life as compared to the liquid formulation (36 months vs 8 months).

A comparative, single-dose and 4-week repeat dose, pharmacokinetic and pharmacodynamic preclinical study of IV administered liquid and lyophilized S95014 formulations was performed in dogs. In this study, lyophilized S95014 has been demonstrated to be equivalent to the original liquid S95014.

S95014 liquid formulation had been authorized by centralized review procedures in 28 countries in the European Union (EU) and 3 countries in the European Economic Area (EEA) in first line treatment of ALL in 2016. The lyophilized formulation of S95014 demonstrated pharmacokinetic/pharmacodynamic comparability through comprehensive analytical and non-clinical comparability assessment recommended by the Committee for Medical Products for Human Use (CHMP) of the European Medicines Agency (EMA). Consequently, the use of lyophilized formulation was approved for S95014 by centralized review procedure in 28 countries in the EU and 3 countries in the EEA in 2017.

2.2.4. Study rationale and design

A phase II, parallel, open-label study, named CL2-95014-002, was set-up to demonstrate the pharmacokinetic comparability of both liquid and lyophilized S95014 formulations in newly-diagnosed paediatric ALL patients.

The present CL2-95014-003 study is designed to provide continued access to S95014 during the consolidation phase in patients who completed the CL2-95014-002 study and who are clinically benefitting from S95014 without major toxicity.

Patients will be administered lyophilized S95014 during the consolidation phase at the dose of 1000, 2000 or 2500 U/m², as per investigator's judgment. Backbone chemotherapy regimen will be administered as per ALL-MB 2015 protocol.

The study will be conducted in compliance with the protocol, GCP, the ethical principles that have their origin in the Declaration of Helsinki and the applicable regulatory requirements.

3. STUDY OBJECTIVES AND ENDPOINTS

The main objective of this roll-over study is to provide continued access to S95014 during the consolidation phase in patients who completed the CL2-95014-002 study and who are clinically benefitting from S95014 without major toxicity.

Secondary objective of this roll-over study is to assess the safety profile of lyophilized S95014 during the consolidation phase. All adverse events regardless of grade or causality and severity will be collected after the informed consent is signed and during the entire treatment period (see [section 8](#)).

4. STUDY DESIGN

4.1. Investigational plan

4.1.1. Study plan

The present CL2-95014-003 study is a multicentre, non-randomized roll-over study of lyophilized Pegasparagase (Oncaspar®, S95014) formulation in the treatment of pediatric patients with ALL who completed the CL2-95014-002 study during the induction phase.

Written informed consent and assent (when appropriate) will be obtained from each patient and/or his/her parent(s)/legal representative during the inclusion visit, corresponding to the withdrawal visit of the initial CL2-95014-002 study.

[figure not shown]
Lyophilized S95014 will be administered every two weeks during the consolidation phase at the dose of 1000, 2000 or 2500 U/m², as per investigator's judgment. Patients will be administered 9 infusions of lyophilized S95014, at week 7, 9, 11, 15, 17, 19, 23, 25 and 27 (3 phases S1, S2 and S3). Patients will receive other backbone chemotherapy agents as per ALL-MB 2015 protocol.

The study duration will be approximately 7 months, including the treatment period consisting of the consolidation phase and the follow-up period. After completing the consolidation phase, patient will be discontinued from the study and will be treated as per investigator's judgment.

For more details about the statistical analyses please refer to the [section 10](#).

The study plan is shown in [Figure \(4.1.1\) 1](#).

Figure (4.1.1) 1 – Study plan

The study will be divided into the following periods for each participant:

- **Inclusion visit:** to obtain informed consent and check the inclusion/non-inclusion criteria. The inclusion visit of CL2-95014-003 study will correspond to the withdrawal visit of the initial CL2-95014-002 study.
- **Treatment period:** As per ALL-MB 2015 protocol, treatment period will start at Day 1 of the consolidation phase. Patients will be on treatment until the end of the consolidation phase, unless they meet a discontinuation criterion as described in [section 5.6.1](#).
- **Withdrawal visit:** up to 30 days after the last dose of S95014 during the consolidation phase. Patient will continue receiving backbone chemotherapeutic regimen as per ALL-MB 2015 protocol, according to physician's judgment.
- **Follow-up visit:** a contact or telephone call will be done approximately 30 days after the last S95014 infusion, except in case of consent withdrawal. Follow-up of adverse events and the patient's survival will be recorded.

The study start is defined as the date of the first visit of the first participant.

End of Trial is defined as the date of the last visit of the last participant (follow-up visit).

In case of non-inclusion of a participant, it is the investigator's responsibility to ensure, in accordance with the local standards of care and medical practices that:

- The reason of non-inclusion is explained to the participant,
- Any event associated with any procedure/condition required by the study protocol (e.g. an event occurring following the discontinuation of a forbidden treatment) is collected,
- An adequate alternative medical care is proposed to the participant.

A non-inclusion visit is not mandatorily carried out, provided these requirements are met and documented in the medical file of the participant.

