6. TREATMENT OF PARTICIPANTS

6.1. IMP and NIMPs administered

6.1.1. IMP

S95014 lyophilizate is considered as the study IMP.

S95014 dosage is calculated according to body surface area (BSA). The BSA will be calculated by the investigator based on the height and weight measured on the day of S95014 infusion (all BSA calculations are rounded to 2 decimal places). Height and weight measured within 3 days before the date of S95014 infusion will be acceptable.

$$\text{BSA (m}^2\text{)} = \sqrt{(\text{Height [cm]} \times \text{Weight [kg]})/3600}$$

Study sites are required to use only calibrated and certified scales throughout the study.

Lyophilized S95014 will be administered IV, over 1 to 2 hours, every two weeks during the consolidation phase at the dose of 1000, 2000 or 2500 U/m², as per investigator's judgment. Patients will be administered 9 infusions of lyophilized S95014, at week 7, 9, 11, 15, 17, 19, 23, 25 and 27 (3 phases S1, S2 and S3). Patients will receive other backbone chemotherapy agents as per ALL-MB 2015 protocol.

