8.10. Management of toxicities

An AE for which a causal relationship to S95014 is evidently ruled out will not be considered toxicity. For patients who do not tolerate the protocol-specified dosing schedule, dose interruptions and/or reductions are either recommended or mandated during the consolidation phase.

The results of laboratory tests should be available before the S95014 administration in order to comply with management of toxicities if applicable.

For each patient, once a dose reduction has occurred, the dose may not be re-escalated during the treatment period unless there is documented agreement with the Sponsor.

Table (8.10) 1 - Criteria for S95014 interruption or discontinuation

Toxicity	Action to be taken
Hypersensitivity	
Grade 1 hypersensitivity	Symptomatic treatment Infusion rate should be reduced by 50%
Grade 2 hypersensitivity	S95014 infusion interruption Symptomatic treatment Upon recovery, infusion can be resumed with an infusion rate reduced by 50%
Grade 3-4 hypersensitivity	S95014 discontinuation Symptomatic treatment Switch to Erwinase should be considered as per investigator's judgment
Pancreatitis	
Grade 2 pancreatitis	S95014 interruption until recovery
Clinical pancreatitis (Grade 3-4)	S95014 discontinuation*
Hepatotoxicity	
Grade 3 ALT and/or AST increase	S95014 interruption, can be resumed if resolved \leq Grade 2
Grade 4 ALT and/or AST increase	If not recovered within 2 weeks: S95014 discontinuation If resolved (\leq Grade 2) within 2 weeks: S95014 can be resumed
Grade 3 total bilirubin increase	S95014 interruption, can be resumed if resolved \leq Grade 2
Grade 4 total bilirubin increase	S95014 discontinuation*
Haemorrhage	
\geq Grade 2 haemorrhage	S95014 interruption until resolves to Grade 1
Grade 4 haemorrhage	S95014 discontinuation
Thrombosis	
Grade 3 thrombotic event	S95014 interruption until recovery
Grade 4 or serious thrombotic event	S95014 discontinuation

**in case of high-risk of relapse, S95014 might be reintroduced at a lower dose as per investigator's judgment*

Prophylactic treatment for hypersensitivity should be administered as per local practice.

For further details about the management of S95014 toxicities, please refer to ALL-MB2015 protocol ([Appendix 1](#)) and [Investigator's Brochure](#).

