1.2.1. Study plan

Written informed consent and assent (when appropriate) will be obtained from each patient and/or his/her parent(s)/legal representative during the inclusion visit, corresponding to the withdrawal visit of the initial CL2-95014-002 study.

S95014 lyophilizate will be administered IV every two weeks during the consolidation phase at the dose of 1000, 2000 or 2500 U/m², as per investigator's judgment. Patients will be administered 9 infusions of S95014 lyophilizate, at weeks 7, 9, 11, 15, 17, 19, 23, 25 and 27. Patients will receive other backbone chemotherapy agents as per ALL-MB 2015 protocol (see study protocol Appendix 1).

The study duration will be approximately 7 months, including the treatment period consisting of the consolidation phase and the follow-up period. After completing the consolidation phase, patient will be discontinued from the study and will be treated as per investigator's judgment.

The study will be divided into the following periods for each participant:

- **Inclusion visit:** to obtain informed consent and check the inclusion/non-inclusion criteria. The inclusion visit of CL2-95014-003 study will correspond to the withdrawal visit of the initial CL2-95014-002 study.
- **Treatment period:** As per ALL-MB 2015 protocol, treatment period will start at Day 1 of the consolidation phase. Patients will be on treatment until the end of the consolidation

[figure not shown]

phase, unless they meet a discontinuation criterion as described in the Clinical Study Protocol.

- **Withdrawal visit:** no later than 30 days after the last dose of S95014 during the consolidation phase. Patient will continue receiving backbone chemotherapeutic regimen as per ALL-MB 2015 protocol, according to physician's judgment.
- **Follow-up visit:** should be made after Withdrawal visit, a contact or telephone call will be done not earlier than 30 days after the last S95014 infusion, except in case of consent withdrawal. Follow-up of adverse events and the patient's survival will be recorded.

The study plan is shown in Figure (1.2.1) 1.

Figure (1.2.1) 1 - Study plan

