3.5.1. Adverse Events

A treatment-emergent adverse event (TEAE) is defined as any untoward medical occurrence in a subject who received IMP (S95014), which occurs within the period from the Inclusion visit, until 30 days after the last S95014 infusion, or the date of withdrawal, whichever is earlier. TEAE will be assessed according to the National Cancer Institute (NCI) Common Terminology Criteria Adverse Events (CTCAE) v5.0. Clinically significant laboratory abnormalities will be classified into Common Terminology Criteria (CTC) grade according to CTCAE v5.0 and will be reported as adverse events if they are associated with signs and symptoms or, clinically significant in the investigator's opinion except if related to the disease, if they require curative therapies, if they induce change of study treatment administration. All analyses described below will be based on TEAEs, if not otherwise specified.

Adverse events will be summarized in hierarchical tables, presenting the number and percentage of subjects having at least one AE, and having at least one AE in each primary system organ class and for each preferred term using MedDRA coding. AEs will be sorted by descending frequency, and alphabetically where frequency is tied. Such summaries will be produced for all AEs, serious adverse events (SAEs), grades 3 or 4 AEs, AEs leading to study treatment discontinuation, and AEs leading to dose-adjustment or interruption of any of the drugs of the treatment. All of these summaries will be by system organ class, preferred term, starting dose level if applicable and, in some case, worst grade. Most of the summaries will be produced twice, once for all events regardless of study treatment relationship, and once for events suspected to be study treatment related. All deaths will be listed and summarized. All AEs will be listed, and any other information collected (e.g., start/end dates and duration of adverse event, severity or relatedness to study medication) will be listed as appropriate.

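### The withdrawal visit and the TEAE window are timed only from the last S95014 infusion, so a hold that ends in permanent discontinuation can outlast both, and new AEs after day 30 then leave the TEAE summaries

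*Protocol*

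**What the plan says.** **Visit timing.** Protocol 4.1.1 places the withdrawal visit "up to 30 days after the last dose of S95014 during the consolidation phase"; SAP 1.2.1 says "no later than 30 days after the last dose of S95014 during the consolidation phase". Protocol 5.6.1, 5.6.2, 5.6.3 and 6.5 deal with early discontinuation and loss to follow-up but give no other timing. Protocol 4.4.1 asks for patients to be seen promptly, but only if the whole study is stopped. Under 5.6.1, stopping the drug early means leaving the study.

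**Analysis window.** SAP 3.5.1 counts TEAEs from the inclusion visit "until 30 days after the last S95014 infusion, or the date of withdrawal, whichever is earlier". It adds: "All analyses described below will be based on TEAEs, if not otherwise specified".

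**Schedule.** Infusions are given "at week 7, 9, 11, 15, 17, 19, 23, 25 and 27" (Protocol 6.1.1).

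**Holds.** For grade 4 ALT/AST, Table (8.10) 1 states "If not recovered within 2 weeks: S95014 discontinuation". For grade 2 pancreatitis and grade 3 thrombosis it states "S95014 interruption until recovery", with no maximum. The holds for grade 3 ALT/AST, grade 3 bilirubin and haemorrhage also have no stated maximum. Any of these can end in discontinuation for an adverse event on the investigator's judgement (5.6.1).

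**Collection.** Protocol 8.9.1 requires all events to be reported up to the withdrawal visit, with no day-30 cap.

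**Follow-up contact.** Protocol 4.1.1 and 8.2 put it at about 30 days after the last infusion, and 8.2 places it after the withdrawal visit. SAP 1.2.1 requires it to follow that visit and to fall no earlier than day 30.

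**The concern.** A limit of 30 days after the last dose works when the last dose is known to be the last. For a patient on hold it is not known. The infusion already given becomes the last one only when permanent discontinuation is decided, and by then the 30 days may have passed.

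Two things follow. The site cannot hold a compliant withdrawal visit for a patient who had not been withdrawn when the visit fell due. And an AE that first starts during the hold, after day 30, is in the database but is not a TEAE, so it is missing from the incidence, SAE, grade 3 or 4 and discontinuation summaries. If that new AE is itself the recorded reason for stopping, the discontinuation table omits it.

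Safety is the only outcome this study assesses (Protocol section 7 marks efficacy as not applicable), so the boundary of the AE tables matters even where few patients are involved.

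**Working it through.** **Inputs**
- Infusion weeks: Protocol 6.1.1 and 4.1.1.
- Visit limit L = 30 days after the last dose: Protocol 4.1.1, SAP 1.2.1.
- Latest end of the TEAE window: day 30, SAP 3.5.1. The alternative end, the date of withdrawal, applies only if earlier, so it can shorten the window but not extend it.
- Fixed wait of 14 days for grade 4 ALT/AST; other holds open-ended: Table (8.10) 1.

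**Assumptions.** Infusions fall on schedule. The hold starts at the pre-dose check for the next infusion, since 8.10 wants laboratory results available before dosing. The 2 weeks run from that check; the table does not say when they start.

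**Formula.** Day of the decision after the last infusion: D = 7 × (next due week − last dosed week) + hold length. Overrun = D − 30 where positive.

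**Step 1: the fixed 2-week wait**

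| Last dose | Next due | Day next dose is due | Days left to day 30 | D with 14-day wait | Result |
|---|---|---|---|---|---|
| W11, W19 | W15, W23 | 7 × 4 = 28 | 30 − 28 = 2 | 28 + 14 = 42 | 12 days over |
| W7, W9, W15, W17, W23, W25 | W9, W11, W17, W19, W25, W27 | 7 × 2 = 14 | 30 − 14 = 16 | 14 + 14 = 28 | 2 days to spare |

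From a scheduled pre-dose check, the fixed rule therefore overruns at two of the eight dose transitions, both at phase boundaries. For a finding on any day x, it overruns when x + 14 > 30, that is, when x > 16.

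**Step 2: open-ended holds.** These pass day 30 after more than 2 days beyond the due date at a phase boundary, or more than 16 days within a phase. The documents give no hold durations, so the lengths below are assumed:

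| Assumed hold (days) | D at boundary | Overrun | D within phase | Overrun |
|---|---|---|---|---|
| 7 | 35 | 5 | 21 | 0 |
| 14 | 42 | 12 | 28 | 0 |
| 21 | 49 | 19 | 35 | 5 |
| 28 | 56 | 26 | 42 | 12 |

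**Step 3: follow the events through.** Last dose W11; grade 4 ALT found on day 28; a separate AE first appears on day 35; discontinuation decided on day 42.
- *The ALT event.* Onset is by day 28, so it is a TEAE. Because it changed study treatment it qualifies as an AE under SAP 3.5.1. The window applies to when the event occurs, not to when action is taken, so it also counts as leading to discontinuation.
- *The day-35 AE, dosing not resumed.* It is reportable under 8.9.1 because the withdrawal visit has not happened. It falls 5 days after the window closed and is in no TEAE-based summary.
- *The same day-35 AE, dosing resumed on day 42.* The last infusion is now day 42 or later, so the AE is a TEAE.
- *The follow-up contact.* At about day 30 under the protocol, it would precede a withdrawal visit that cannot take place before day 42.

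**Step 4: origin of the cut-off.** Protocol 10.2.1.1 tabulates AEs without a time window, and the synopsis names TEAEs without defining them. The cut-off enters through SAP 3.5.1.

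**The case against.** The strongest reply is that a 30-day window from last exposure matches the protocol's own window for immediately notifiable events (8.9.1) and its 30-day follow-up period. Any window anchored on the last dose treats resumed and non-resumed patients differently. Stretching it with the hold would give unequal observation times and take in more events due to the backbone chemotherapy, which continues. That stands, and it is a good reason to leave the main TEAE window alone.

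It also stands that the fixed rule overruns at only two transitions, that laboratory tests between visits (8.2) may reveal a toxicity earlier, and that the SAP already orders the follow-up contact correctly.

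Three stronger readings are tempting, and the documents do not support them:
- *That the tables hide the toxicity that ended treatment.* A hold begun at a scheduled check starts by day 28, so the triggering event is normally inside the window and is counted.
- *That an event turning serious during the hold is lost.* Protocol 8.9.2.2 records changes in intensity, seriousness or outcome on the page already opened for that event. An AE with onset by day 30 remains one TEAE with its updated seriousness.
- *That later AEs vanish from every output.* SAP 3.5.1 says that all AEs are listed and all deaths are listed and summarised. The listings are unaffected, and the death summary may be too; the SAP does not say whether the TEAE default reaches it.

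The reply does not answer the visit timing, nor the AE with first onset after day 30 in a patient who never restarts.

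**Conclusion.** The gap is real and narrow. Under the documents' own schedule and hold rules, discontinuation can be decided on day 42 against a limit of day 30. The withdrawal visit is then overdue before the patient has been withdrawn. AEs with first onset from day 31 to that visit are collected but left out of the TEAE-based summaries if dosing does not resume. The gap is 12 days in the grade 4 ALT/AST case at W15 or W23. For open-ended holds it depends on a duration that the documents do not give: 5 to 26 days at a phase boundary for assumed holds of 7 to 28 days.

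This rests on infusions falling on schedule and holds starting at the pre-dose check. How many of the approximately 88 planned patients would be affected cannot be computed, because no hold or discontinuation rates are stated. The point warrants a wording correction. It does not show that the main AE tables misstate the toxicities that led to holds.

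**What to change.** **Visit timing (Protocol 4.1.1, SAP 1.2.1).** For patients who stop early, time the withdrawal visit from the decision to discontinue permanently, within a number of days that the sponsor sets. Keep the last-dose anchor for completers. Align the protocol's follow-up contact (4.1.1 and 8.2) with the SAP: after the withdrawal visit and not before day 30.

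**Analysis (SAP 3.5.1).** Count any AE recorded as leading to S95014 discontinuation in that table, whatever its onset day. Summarise separately AEs with onset after day 30 and up to the withdrawal visit. Leave the main TEAE window unchanged.

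**To reconcile.** The sponsor should reconcile Protocol 4.1.1, 8.2, 8.9.1 and Table (8.10) 1 with SAP 1.2.1 and 3.5.1. No hold duration or stopping rule is proposed here.

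**Cost.** Wording in two documents and one small extra summary, from data that 8.9.1 already requires; no added visit. The downside is that this summary may include events due to backbone chemotherapy and covers a period that differs between patients, so it should be labelled as supplementary.
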